4.3 Other Clinical Outcomes Assessments

4.3.1 Daily Ulcerative Colitis Scale for Children and Caregivers (DUCS)

Shire has developed an electronic daily sign and symptom diary, the DUCS. Two versions have been developed: 1 PRO to be self-completed by children aged 8-17 years and 1 ObsRO to be completed by caregivers of children aged 5-10 years. Both the PRO and ObsRO will be completed by children aged 8-10 years; however, the ObsRO will be used for the secondary endpoint analysis. The data obtained from the PRO in this age group will provide information for future use to determine if children/adolescents can reliably complete the PRO.

A separate SAP has been developed for DUCS.

4.3.2 Overall Current Health

An Overall Current Health item will be included in the e-diary. The Overall Current Health item has been tested in cognitive debriefing interviews with the DUCS.

4.3.3 Global Change in Health

The Global Change in Health item assesses the subject's (aged 11-17 years) or caregiver's (for children aged 5-10 years) perception of change in health since starting the study and will be administered via paper in this study. This item has been tested in cognitive debriefing interviews with the DUCS.

4.3.4 Pediatric Ulcerative Colitis Activity Index

The PUCAI is a physician-administered measure that focuses on 6 key signs and symptoms of UC and activity limitations ([Turner et al., 2007](#)). The PUCAI yields a total score ranging from 0-85 with higher scores being worse. Recommended cut-off scores to differentiate disease activity are <10 (remission); 11-30 (mild); 31-64 (moderate) and >65 (severe) ([Turner et al., 2009](#)). Evaluation of the construct validity of the PUCAI revealed that it was highly correlated with physician's global assessment of disease activity and PUCAI scores were highly predictive of the need for escalating medical therapy ([Turner et al., 2009](#)).

Only sites who have executed a sub-license with Shire for PUCAI use will be able to collect PUCAI data for the study.

Item	Points
1. Abdominal pain	
No pain	0
Pain can be ignored	5
Pain cannot be ignored	10
2. Rectal bleeding	
None	0
Small amount only, in less than 50% of stools	10
Small amount with most stools	20
Large amount (>50% of the stool content)	30
3. Stool consistency of most stools	
Formed	0
Partially formed	5
Completely unformed	10
4. Number of stools per 24 hours	
0–2	0
3–5	5
6–8	10
>8	15
5. Nocturnal stools (any episode causing wakening)	
No	0
Yes	10
6. Activity level	
No limitation of activity	0
Occasional limitation of activity	5
Severe restricted activity	10
Sum of PUCAI (0–85)	

© Copyright to The Hospital for Sick Children,
Toronto, Canada, 2006.

4.3.5 IMPACT III

The IMPACT questionnaire is a disease-specific health-related quality-of-life questionnaire developed for use in pediatric inflammatory bowel disease through a process of patient interviews and analysis of patient responses to an item-reduction questionnaire. This is a self-administered questionnaire, and data will be collected via paper in this study.

The IMPACT questionnaire has been studied to determine its feasibility, reliability, and validity. It was found to be a valid and reliable reflection of health-related quality of life of older children and adolescents with both UC and Crohn's disease ([Otley et al., 2002](#)).

In this study, the IMPACT III will be used. This is the current version of the questionnaire, adapted from IMPACT II, which was developed in 2002. The original version of IMPACT was developed in 1999. IMPACT III contains 35 items in 6 domains. The Bowel Symptoms domain and the 4 matching symptom items between the IMPACT III and the DUCS will be used to evaluate convergent validity of the DUCS.

The IMPACT III questionnaire has 35 questions, each with 5 Likert responses that are scored 1, 2, 3, 4, or 5, such that a higher score corresponds to a better quality of life. The questions are grouped into 5 domains, each of which is scored by adding the scores of the questions therein. A total score is obtained by adding the scores of all of the questions. The total score and the domain scores are computed only if the number of missing responses is no more than the maximum number in the table below.

Domain Name (range of scores)	Question numbers (Maximum number of missing responses)
Body Image (3 – 15)	7, 15, 33 (0)
Bowel Symptoms (7 – 35)	1, 3, 10, 19, 21, 25, 31 (1)
Emotional Functioning (7 – 35)	4, 5, 11, 12, 13, 16, 29 (1)
Social Functioning (12 – 60)	8, 9, 14, 17, 18, 20, 23, 26, 27, 30, 34, 35 (1)
Systemic Symptoms (3 – 15)	6, 28, 32 (0)
Treatment/Interventions (3 - 15)	2, 22, 24 (0)
Total Score (35 – 175)	1 – 35 (3)

The IMPACT is valid for children and adolescents aged 9-17 years old and is completed by the subject. Children/adolescent aged 9-17 years who cannot complete the questionnaire independently, may be assisted by an adult who is not the child's guardian or relative. Children who are 8 years old may complete the IMPACT with assistance from an adult who is not the child's guardian or relative. Children under the age of 8 years old will not complete the IMPACT.

4.4 Safety Assessments

4.4.1 Medical and Medication History

At screening, the subject's medical history (including UC history) and concomitant medications will be reviewed. Any new medical events or changes in intensity from the Screening Visit (Visit 1) noted during the study should be evaluated for report as an AE. New medications or changes to existing medications must be added or updated as appropriate. Adverse Event Assessments

At each study visit, subjects will be questioned in a general way to ascertain if AEs have occurred since the previous visit (e.g., “Have you had any health problems since your last visit?”). Adverse events are collected from the time informed consent is signed.

In addition, any symptoms/conditions reported during assessments or collected via structured data collection will be evaluated by the investigator at each study visit to determine whether these are AEs.

4.4.2 Vital Signs

Vital signs include blood pressure and pulse. Blood pressure should be determined by cuff (using the same method, the same arm, and in the same position throughout the study). Any clinically significant deviations from the Baseline Visit (Visit 2) vital signs which are deemed clinically significant in the opinion of the investigator are to be recorded as an AE.

Measurements of vital signs (blood pressure and pulse) will be performed at all study visits. Blood pressure and pulse will be determined in the sitting position (after 5 minutes).

4.4.3 Height and Weight

Height will be assessed at the Screening Visit (Visit 1) and at the final visit of each phase. Weight will be assessed at the Screening Visit (Visit 1), the Baseline Visit (Visit 2) and at the final visit of each phase.

4.4.4 Clinical Laboratory Evaluations

All clinical laboratory assays will be performed according to the laboratory’s normal procedures. Reference ranges are to be supplied by the laboratory and will be used to assess the clinical laboratory data for clinical significance and out-of-range pathological changes.

The investigator should assess out-of-range clinical laboratory values for clinical significance, indicating if the value(s) is/are not clinically significant or clinically significant. Abnormal clinical laboratory values, which are unexpected or not explained by the subject’s clinical condition, may, at the discretion of the investigator or sponsor, be repeated as soon as possible until confirmed, explained, or resolved.

The following routine clinical laboratory assessments will be performed:

Biochemistry	Hematology
ALT Albumin Alkaline phosphatase AST Bilirubin, total Bicarbonate Calcium Chloride Cholesterol, total Creatinine, enzymatic CK (creatine kinase) CRP standard (C-reactive protein) Direct bilirubin Gamma GT Glucose random, serum Lactate dehydrogenase Magnesium Phosphate Potassium Sodium Total protein Triglycerides Urea (BUN, blood urea nitrogen) Uric acid	Complete blood count (RBC [red blood cells], WBC [white blood cells], platelets, HGB [hemoglobin]) HCT (hematocrit) White blood cell differential

Microscopic examination will be conducted if protein and/or blood is/are detected during urinalysis. The microscopic examination will consist of red blood cells, white blood cells, casts, and bacteria.

4.4.5 Pregnancy Test

A serum β -HCG pregnancy test is performed for all females of childbearing potential at the following visits as applicable to the subject's participation in the study:

- Screening Visit (Visit 1)
- Double-blind Acute Phase: Week 8 (Visit 3.2)
- Open-label Acute Phase: Week 8 (Visit 4.2)
- Double-blind Maintenance Phase: Week 26 (Visit 5.2)
- If pregnancy is suspected
- On withdrawal of the subject from the study

A urine pregnancy test is performed for all females of childbearing potential at all other visits as indicated in [Table 5](#), [Table 6](#), and [Table 7](#).

4.4.6 Stool Assessments

Collection of stool samples for all assessments must occur before administration of any bowel preparations for endoscopy if samples are collected on the same day as bowel preparation administration.

If a standard of care stool sample has been collected within 24 hours prior to the Screening Visit (Visit 1), this sample may be used for screening assessments and evaluations provided that written informed consent/assent has been collected before the stool is sent for laboratory analysis.

Screening Assessments

A stool sample will be collected during the Screening Visit (Visit 1), which is a period of 3 to 21 days. If a standard of care stool sample was collected within 24 hours prior to the Screening Visit (Visit 1), this sample may be used for screening assessments and evaluations. The sample must be collected in sufficient time to ensure results reporting within the Screening Visit (Visit 1) period. Stool samples collected for culture may be processed by local laboratories; however, results from the central laboratory analysis will prevail and will be entered into the eCRF. The following parameters will be assessed:

- Culture for enteric pathogens including *Salmonella*, *Shigella*, *Yersinia*, *Aeromonas*, *Plesiomonas*, and *Campylobacter*
- Presence of *Clostridium difficile* toxin
- Microscopic examination of stool for ova and parasites.

If the stool sample is positive for any of the above parameters, the subject will not be eligible for the study.

4.4.7 Physical Examinations

Abnormalities identified at the Screening Visit (Visit 1) will be documented in the subject's source documents. Changes after the Screening Visit (Visit 1) will be captured as AEs, as deemed by the investigator.

4.4.8 Pharmacokinetic Assessments

Blood samples will be collected at the times specified in [Table 5](#), [Table 6](#), and [Table 7](#) to allow measurement of plasma concentrations of 5-ASA and its major metabolite Ac-5-ASA.

Pharmacokinetic sampling will occur only at participating sites that have been appropriately assessed and qualified for pharmacokinetic sampling.

5. STATISTICAL ANALYSIS

5.1 General Methodology

All statistical analyses will be performed using SAS® Version 9.2 or higher (SAS Institute, Cary, North Carolina, USA).

Unless otherwise specified, summary tabulations using the Double-blind Acute Phase and Double-blind Maintenance Phase Safety Analysis Sets will be presented by treatment arm and overall. Summary tabulations using the Open-label Acute Phase Safety Analysis Set will be presented by high-dose only. Summary tabulations using the Overall will be presented by overall only.

For categorical variables, the number and percentage of subjects within each category (with a category for missing data as needed) of the parameter will be presented. For continuous variables, the number of subjects, mean, median, standard deviation (SD), Q1, Q3, minimum, and maximum values will be presented.

This is an estimation study intended to provide estimates of clinical response for 2 doses (low and high) across a range of weight groups and not powered to detect differences between treatment groups. P-values will be presented as descriptive statistics.

All statistical tests will be 2-sided hypothesis tests performed at the 5% level of significance for main effects. All confidence intervals will be 2-sided 95% confidence intervals, unless stated otherwise.

5.2 Subject Population Sets

Note that as the efficacy analysis sets are identical to the safety sets for this study, only one set of definitions will be used. All efficacy analyses will be based on the Safety Analysis Sets.

5.2.1 Screened Set

The Screened Set will consist of all subjects who have signed an informed consent.

5.2.2 Enrolled Set

The enrolled Set will consist of all subjects who have signed informed consent and also passed inclusion/exclusion criteria.

5.2.3 Overall Randomized Analysis Set

The Overall Randomized Analysis Set will consist of randomized subjects.

5.2.4 Overall Safety Analysis Set

The Overall Safety Analysis Set will consist of randomized subjects who have taken at least 1 dose of investigational product.

5.2.5 Double-blind Acute Phase Safety Analysis Set

The Double-blind Acute Phase Safety Analysis Set will consist of randomized subjects who have taken at least 1 dose of investigational product during the Double-blind Acute Phase.

5.2.6 Open-label Acute Phase Safety Analysis Set

The Open-label Acute Phase Safety Analysis Set will consist of all subjects who have taken at least 1 dose of investigational product during the Open-label Acute Phase.

5.2.7 Double-blind Maintenance Phase Safety Analysis Set

The Double-blind Maintenance Phase Safety Analysis Set will consist of randomized subjects who have taken at least 1 dose of investigational product during the Double-blind Maintenance Phase.

5.3 Subject Disposition

A listing of all Screen Failures (i.e., subjects who were screened but not randomized) will be presented along with reasons for screen fail and details of any adverse events (AEs).

The number of subjects included in each analysis set (i.e., Screened Set, Enrolled Set, Overall Randomized Analysis Set, Overall Safety Analysis Set, Double-blind Acute Phase Safety Analysis Set, Open-label Acute Phase Safety Analysis Set, and Double-blind Maintenance Phase Safety Analysis Set) will be summarized as a whole. For the Double-blind Maintenance Phase Safety Analysis Set, this will also include the subjects who entered directly, and subjects who entered via the Acute Phase (Double-blind/Open-label) as well as the total.

For Double-blind Acute Phase and Double-blind Maintenance Phase Safety Analysis Sets, the number and percentage of subjects who completed, and discontinued from the phase will be presented by treatment arm and overall. For the Open-label Acute Phase Safety Analysis Set, the number and percentage of subjects who completed, and discontinued from the phase will be presented by high dose only. The Primary reasons for discontinuation as recorded on the termination page of the electronic case report form (eCRF) will also be summarized (number and percentage) by treatment arm, separately for each phase. All subjects who discontinued will be listed by discontinuation reason, separately for each phase.

The number of subjects enrolled, randomized, received at least 1 dose of investigational product and completed will be tabulated by site and country for the Overall Randomized Analysis Set. In addition, the duration of enrollment in days, will be summarized for each site, country, and overall. Duration of enrollment will be calculated as (last date of contact for any subject at that site - the first date of informed consent for any subject at that site + 1).

5.4 Protocol Violations and Deviations

Protocol major/minor deviations will be recorded by the site separately from the clinical database. The Shire study team will review and classify all protocol deviations and violations into categories before database lock.

Protocol deviations will be summarized by site for Overall Safety Analysis Set and Open-Label Acute Phase Safety Analysis Set. Protocol deviations will also be summarized by site and treatment arm for the Double-blind Acute Phase Safety Analysis Set and the Double-blind Maintenance Phase Safety Analysis Set separately. Protocol major/minor deviations will be also listed.

5.5 Demographic and Baseline Characteristics

Descriptive summaries of demographic and baseline characteristics will be presented separately for each Safety Analysis Set (Overall, Double-blind Acute Phase, Open-label Acute Phase and Double-blind Maintenance Phase). For the Double-blind Acute Phase and Double-blind Maintenance Phase Safety Analysis Sets, summaries will be presented by treatment arm and overall. For the Overall Safety Analysis Set, summaries will be presented by overall, and for the Open-label Acute Phase Safety Analysis Set, summaries will be presented for high-dose only.

Demographic characteristics include age, age group (5-10 years and 11-17 years), sex, ethnicity, and race. Baseline characteristics include weight, weight group (18 to \leq 23kg, >23 to \leq 35kg, >35 to \leq 50kg and >50 to \leq 90kg), height, and body mass index (BMI). Height will be presented in cm and weight will be presented in kg. Any height measurements recorded in the CRF in inches will be multiplied by 2.54 to convert to cm. Body mass index will be presented in kg/m².

Ulcerative colitis history will be presented separately for each Safety Analysis Set (Overall, Double-blind Acute Phase, Open-label Acute Phase, and Double-blind Maintenance Phase). For the Double-blind Acute Phase and Double-blind Maintenance Phase Safety Analysis Sets, summaries will be presented by treatment arm and overall. For the Overall Safety Analysis Set, summaries will be presented overall only, and for the Open-label Acute Phase, summaries will be presented for high-dose only.

The following parameters will be summarized:

- Time (in months) since diagnosis ([screening date - diagnosis date] +1 / 30)
- Method of diagnosis
- Diagnosis state (i.e., is the subject newly diagnosed)

For subjects who are not newly diagnosed:

- Number of acute episodes of UC in the last year
- Number of acute episodes of UC since diagnosis
- Typical duration of past acute episodes (days [where this is recorded in weeks the value will be multiplied by 7])
- Time (in days) since current acute episode of UC ([screening date - onset date] +1)
- Full extent of disease measured from anal margin (cm) at the time of the most recent endoscopy
- The classification of the extent of disease at the most recent endoscopy
- Subjects with rectal involvement
- Subjects with extra-intestinal manifestations
- Subjects with any history of significant GI surgery

Medical history will be listed.

5.6 Extent of Exposure and Treatment Compliance

For the Double-blind Acute and Double-blind Maintenance Phase, summaries will be presented by treatment arm and overall. For the Open-label Acute Phase, summaries will be presented by treatment arm only.

5.6.1 Exposure to Investigational Product

Exposure to investigational product will be summarized separately for each of the three Safety Analysis Sets (Double-blind Acute Phase, Open-label Acute Phase and Double-blind Maintenance Phase). Summary statistics (n, mean, SD, median, Q1, Q3, minimum, and maximum) for the duration of treatment exposure will also be presented.

Exposure will be summarized in terms of total dose, average daily dose, and length of exposure for each phase, calculated for each subject as:

- Total Dose (mg) = sum of doses within phase of interest
- Average Daily Dose (mg/day) = Total Dose / total days of dosing within phase of interest
- Length of Exposure (weeks) = (Date of last dose within phase of interest – date of first dose within phase of interest + 1) / 7

Additionally, to examine subject-level exposure across study phases, these parameters will be listed by subject and phase.

5.6.2 Measurement of Treatment Compliance

Summaries of compliance will be produced for each of the three Safety Analysis Sets (Double-blind Acute Phase, Open-label Acute Phase and Double-blind Maintenance Phase).

Frequencies and percentages of subjects will be presented for the following categories: <80%, 80-120%, and >120%. Any treatment compliance calculations conducted at the site will be used for study management purposes. Therefore, those values will not be reconciled with values calculated during data analysis. Summary statistics (n, mean, SD, median, Q1, Q3, minimum, maximum) will also be presented.

Compliance is calculated for each phase and defined as:

$$\frac{\text{Overall Number of tablets dispensed} - \text{Overall Number of tablets returned}}{[\text{Date of Last Dose} - \text{Date of First Dose} + 1] \times \text{Number of Tablets Per Day}} \times 100 \%$$

The number of tablets per day is 4 for subjects in the weight groups of 18 to $\leq 23\text{kg}$, >23 to $\leq 35\text{kg}$, and >50 to $\leq 90\text{kg}$ regardless of treatment arm or phases. The number of tablets per day is 6 for subjects in the >35 to $\leq 50\text{kg}$ weight group regardless of treatment arm or phases.

Additionally, to examine subject-level compliance across study phases, these parameters will be listed by subject and phase.

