6.2.3 Dosing

Subjects entering the Double-blind Acute Phase or entering the Double-blind Maintenance Phase directly will be randomized to low- or high-dose MMX mesalamine/mesalazine stratified by their weight group at the Baseline Visit (Visit 2).

Subjects entering the Double-blind Maintenance Phase after completing 1 or both of the Acute Phases will be re-randomized to low- or high-dose MMX mesalamine/mesalazine at the start of the Double-blind Maintenance Phase at Visit 3.2 (Week 8 of the Double-blind Acute Phase) or 4.2 (Week 8 of the Open-label Acute Phase), as applicable, based on their weight at the time of re-randomization.

Doses will be as follows:

- 900 or 1800mg/day for subjects weighing 18 to \leq 23kg
- 1200 or 2400mg/day for subjects weighing >23 to \leq 35kg
- 1800 or 3600mg/day for subjects weighing >35 to \leq 50kg
- 2400 or 4800mg/day for subjects weighing >50 to \leq 90kg.

Subjects participating in the Open-label Acute Phase will receive the high dose for their weight group. The subject's weight at Visit 3.2 (Week 8/Withdrawal of the Double-blind Acute Phase) will be used to determine the high dose assigned to the subject.

Investigational product will be administered orally, once daily, in accordance with the MMX Mesalazine (Mesalamine) Investigator's Brochure. No titration or dose adjustment is allowed.

Dosing with investigational product will begin the day of the Baseline Visit (Visit 2) if the subject's currently prescribed 5-ASA treatment (if applicable) has not yet been taken that day. If the subject's currently prescribed 5-ASA treatment (if applicable) has been taken the day of the Baseline Visit (Visit 2), dosing with investigational product will begin the day after the Baseline Visit (Visit 2).

When proceeding through study phases, dosing with newly prescribed investigational product will begin the day of the study visit if the subject's currently prescribed investigational product from the current phase has not yet been taken that day. If the subject's currently prescribed investigational treatment has been taken the day of the study visit, dosing with newly prescribed investigational product will begin the day after the first study visit of the new phase.

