6.3.2 Packaging

Double-blind investigational product is packaged in blister pack wallets containing a 1-week supply of product (tablet quantity dependent on weight group). Placebo, which exactly matches the investigational product, will be used in the blister packs to provide the same number and size tablets for each of the doses within a weight group and maintain the blind between the low and high dose groups.

Open-label investigational product is packaged in 100cc high-density polyethylene bottles in the following counts:

- 600mg=60 tablets/bottle
- 1200mg=40 tablets/bottle

Changes to sponsor-supplied packaging prior to dosing may not occur without full agreement in advance by the sponsor.

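### The fixed compliance divisor of 4 tablets a day for the 18 to ≤23 kg group does not fit the open-label supply listed in the protocol

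*SAP*

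**What the plan says.** SAP 5.6.2 defines compliance as tablets dispensed minus tablets returned, divided by days of dosing times tablets per day, times 100%. The tablets-per-day term is fixed by weight group: "The number of tablets per day is 4 for subjects in the weight groups of" 18 to ≤23 kg, >23 to ≤35 kg and >50 to ≤90 kg, and 6 for >35 to ≤50 kg. Both counts apply "regardless of treatment arm or phases".

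The open-label phase is in scope: "Summaries of compliance will be produced for each of the three Safety Analysis Sets", and SAP Section 10 lists an open-label compliance table (14.3.8.2). Results are banded: "Frequencies and percentages of subjects will be presented for the following categories: <80%, 80-120%, and >120" per cent. Subject-level values are also listed by phase. Compliance values calculated at the site are for study management, and "those values will not be reconciled with values calculated during data analysis".

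On dose, Protocol 6.2.3 states: "Subjects participating in the Open-label Acute Phase will receive the high dose for their weight group". The entry for the lightest group begins "900 or 1800mg/day for subjects weighing 18 to" and ends at ≤23 kg, so its high dose is 1800 mg/day. SAP Table 1 gives the same figure.

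On supply, Protocol 6.3.2 says: "Open-label investigational product is packaged in 100cc high-density polyethylene bottles in the following counts", and then lists 600 mg (60 per bottle) and 1200 mg (40 per bottle). Protocol 6.1 says that the study product comes in 300, 600 and 1200 mg tablets. Protocol 6.1.1 and 6.3.2 describe placebo fill for the double-blind blister packs; neither mentions it for the open-label bottles.

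**The concern.** A fixed count across arms is sound in the double-blind phases, because placebo equalises the number of tablets within a weight group. Extending it to all phases carries it into a phase that has no described placebo fill and no listed 300 mg tablet. For the lightest group the count then cannot match any way of making the stated dose.

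At stake is the accuracy of one descriptive table and one listing. A child who takes every tablet would appear in the lowest band. The by-phase listing, which is meant to show how a subject's compliance changes across phases, would show a drop on entering open label that reflects only the divisor. The distortion also runs the other way, because overuse can be placed in the middle band. Since site values are not reconciled with the analysis values, the compliance section has no step that would catch this.

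**Working it through.** **Inputs**
- Divisor for 18 to ≤23 kg: 4 tablets/day, all phases (SAP 5.6.2).
- Open-label dose for this group: 1800 mg/day (Protocol 6.2.3; SAP Table 1).
- Listed open-label strengths: 600 mg and 1200 mg (Protocol 6.3.2).
- Phase length: 8 weeks = 56 days.
- Bands: <80%, 80-120%, >120% (SAP 5.6.2).

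**Step 1. Reproduce the SAP's 4 in the double-blind phases.** With 300, 600 and 1200 mg tablets, 2 × 300 + 2 × 600 = 1800 mg is four active tablets. The low dose of 900 mg is one 300 and one 600 active with two placebos. The divisor of 4 therefore works for this group in both double-blind phases.

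**Step 2. Try 4 in the open-label phase.** Four tablets drawn from 600 and 1200 mg total 2400, 3000, 3600, 4200 or 4800 mg, never 1800 mg. The only ways to make 1800 mg are:
- 3 × 600 mg = 3 tablets;
- 1 × 600 + 1 × 1200 mg = 2 tablets.

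**Step 3. Apply the SAP formula at full adherence over 56 days.**
- 3 tablets: (3 × 56)/(4 × 56) = 168/224 = 75%.
- 2 tablets: (2 × 56)/(4 × 56) = 112/224 = 50%.

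Both fall in the <80% band, so the result does not depend on which combination is dispensed.

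**Step 4. See what the bands mean with 3 tablets prescribed.** True intake as a share of the prescribed count = reported value × 4/3.
- Reported 80% = 106.7% of the prescribed count.
- Reported 100% = 133.3%.
- Reported 120% = 160%.

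The 80-120% band would thus hold children taking between 106.7% and 160% of what was prescribed.

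**Step 5. Check the other groups.** Their fixed counts can be met from the listed open-label stock: 4 × 600 = 2400 mg, 6 × 600 = 3600 mg, 4 × 1200 = 4800 mg. The documents do not say which strengths are dispensed, and other combinations are possible. For example, 2 × 1200 = 2400 mg would give 2/4 = 50% at full adherence.

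**Step 6. Recompute with the prescribed count as divisor.** 168/168 = 100% and 112/112 = 100%; both fall in the 80-120% band.

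**The case against.** The strongest objection is that the fault may lie in the protocol's packaging text rather than in the SAP. Protocol 6.3.2 lists two bottle strengths but does not say that they are the only ones, and Protocol 6.1 does not restrict the 300 mg tablet to a phase. If 300 mg tablets were also supplied open-label, 2 × 300 + 2 × 600 mg makes 1800 mg from four tablets and the SAP sentence is right. The SAP was written against the 10 Apr 2017 protocol and names all phases explicitly. This stands: the documents establish a mismatch, not which text is wrong.

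The number affected may also be zero. The minimum of 2 subjects in this weight group (Protocol Table 4) is an enrollment floor for both doses combined, not a count of open-label entrants. An affected child must enter the Double-blind Acute Phase, move to open label, and still weigh ≤23 kg at Visit 3.2, because that weight sets the open-label dose. This stands too.

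Finally, little depends on the figure. No analysis set, efficacy endpoint or sensitivity analysis uses compliance, and the open-label phase has a single arm, so no dose comparison is distorted. SAP 5.6.1 reports exposure in mg by subject and phase with formulas that do not use this divisor, so a reader could cross-check a suspicious 75%. All of this limits the size of the point but does not make the compliance figure correct.

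A reader might infer that every child in this group is certain to be reported as non-compliant. The documents do not support that. It would require Protocol 6.3.2 to be a complete supply list, and the SAP treats <80% as a descriptive band without calling it non-compliance.

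**Conclusion.** The point holds as an inconsistency between the SAP's compliance divisor and the protocol's dosing and packaging text, confined to the 18 to ≤23 kg group in the Open-label Acute Phase. The error in the reported percentage is large for any subject it reaches (25 or 50 percentage points at full adherence), but it reaches few subjects or none and touches only descriptive output. It is a minor correction.

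The conclusion rests on two assumptions: that the 600 mg and 1200 mg bottles are all that is supplied open-label, and that no placebo is added in that phase. No other section gives an open-label tablet count that would contradict them.

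**What to change.** Reconcile SAP 5.6.2 with Protocol 6.2.3 and 6.3.2.
- If the packaging list is complete, amend SAP 5.6.2 so that, for the Open-label Acute Phase, the divisor is the number of tablets per day actually prescribed to the subject rather than a fixed count for all phases. This also covers the other weight groups, whichever strengths they are given.
- Compliance as mg used divided by mg prescribed is an alternative, provided that tablet strength is captured in the data. Protocol 6.4 requires dispensed medication to be documented but does not say that strength is recorded, so this needs checking first.
- If 300 mg tablets are in fact supplied open-label, correct the packaging text in Protocol 6.3.2 instead. A divisor based on the prescribed count would still be correct.

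The cost is one sentence in the SAP, or one line in the protocol, plus a check of how the open-label product is dispensed. No dose, visit or endpoint changes.
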